2.9 Statistical Methods

Unless specified otherwise, SAS® Version 9.4 or higher will be utilized to perform the statistical analyses of efficacy and safety measures.

Per the protocol, subjects who met all eligibility criteria were to receive single dose injections of 3,500 Units of MYOBLOC every 13 weeks (± 2 weeks) over a maximum possible duration of 1 year, for up to a total of 4 treatments via injections into the submandibular and parotid glands. Repeat injections at each treatment session were to be done when subjects returned to baseline status as determined by the Investigator, with a minimum interval of 11 weeks from the prior injection. If after the first treatment of 3,500 Units the subject developed intolerable side effects, but still wished to remain in the study, the Investigator had the discretion to decrease subsequent doses, but to no less than a total dose of 2,500 Units. Since the majority of subjects received 3500 Units, all statistical tables will present results under one treatment group labeled "Any Dose". Additionally, listings will be categorized as L = low dose (1500-2000 U); M = medium dose (2500-3000 U); H = high dose (3500 U).

Categorical variables will be summarized in general using frequencies and percentages, whereas continuous variables will be summarized in general using descriptive statistics of number of observations (n), mean, standard deviation (SD), minimum (Min), median, and maximum (Max).

In both data listings and CRF domain data tabulations, subject ID will consist of site number plus the assigned subject number.

Hypothesis testing, unless otherwise indicated, will be performed at the 5% significance level. All p-values will be rounded to four decimal places; p-values less than 0.001 will be presented as '<0.001' in all tables. All confidence intervals will be two-sided with 95% coverage.

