13.2 Study Drug Administration and Compliance

Subjects will receive single dose injections of MYOBLOC every 13 weeks (± 2 weeks) for a maximum total of 4 treatments. MYOBLOC will be injected first into the submandibular glands (right and then left) followed by the parotid glands (right and then left)

- Total dose of 3,500 Units (0.7 mL) of MYOBLOC with 1,500 Units (0.3 mL) injected into each parotid gland and 250 Units (0.05 mL) injected into each submandibular gland.

Subsequent injections at each treatment session will be done when subjects return to baseline status as determined by the Investigator, with a minimum interval of 11 weeks from the prior injection. Study drug injections should not be administered if an adverse event of dysphagia or dry mouth of moderate to severe severity persists without prior consultation with the Medical Monitor. If the adverse event has not resolved or has not improved to a mild severity by the end of the per protocol window for injections to occur (every 13 ± 2 weeks), the Medical Monitor should be contacted to discuss whether or not the subject should be dosed, discontinued, etc.

If after the first treatment of 3,500 Units the subject develops intolerable side effects, but still wishes to remain in the study, the Investigator has the discretion to decrease subsequent doses, but to no less than a total dose of 2,500 Units. If this does occur, the total dose can therefore be 2,500 Units to 3,500 Units of MYOBLOC. The Investigator must clearly indicate the adjusted dose given. MYOBLOC will be injected first into the submandibular glands (right then left) followed by the parotid glands (right then left) as follows:

- Total dose of 2,500 to 3,500 Units (0.5 mL to 0.7 mL) of MYOBLOC with 1,000 to 1,500 Units (0.2 mL to 0.3 mL) injected equally into each parotid gland and 250 Units (0.05 mL) injected into each submandibular gland.

All MYOBLOC injections will be performed by Investigators who have prior experience or have been appropriately trained with injecting botulinum toxin and such experience/training will be documented in the study records. Injections will be guided by external anatomical landmarks or by external anatomical landmarks with ultrasound-guided confirmation (Appendix A). Sites designated as “ultrasound” sites will perform all their injections with ultrasound-guidance.

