17.3 Analysis Populations

All subjects who return to the clinic on Day 1 (i.e., study baseline) and have all required baseline (before injection of study drug) assessments/procedures completed will be considered study participants. Study populations, identified and finalized before the database lock, are as follows:

Safety Population

This population is defined as all subjects who are injected with at least 1 dose of study drug. Where applicable, subject grouping will be based on the actual doses the subject received at each session and grouped into 3 groups: low dose (2,500 to 2,999 Units), medium dose (3,000 to 3,499 Units), and high dose (3,500 Units).

Intention-to-Treat (ITT) Population

This population is defined as all subjects who are injected with study drug and have at least 1 post-baseline measurement recorded in the eCRF for both USFR and CGI-C. The ITT population will be used for effectiveness analyses.

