17.7 Statistical Methods for Safety

Frequency of treatment-emergent adverse events (TEAEs) will be calculated for each body system, by preferred term, and by treatment session, for number of subjects and proportion reporting the event and AESI. The incidence of subjects reporting TEAEs will also be reported without those TEAEs categorized as related to the primary underlying disease conditions by the Investigator. The severity of the adverse events and the relationship to study drug will be summarized for each body system and preferred term. Withdrawals due to adverse events will be summarized for each body system and preferred term. Narratives will be presented for all deaths, subjects reporting SAEs, and subjects withdrawn due to adverse events.

Vital signs and weight will be summarized descriptively for continuous variable at each pre-injection visit (i.e., Day 1, Weeks 13, 26, and 39) and at each post-injection time point of 4 weeks post-injection (i.e., Weeks 4, 17, 30, and 43), 8 weeks post-injection (i.e., Week 8, first Treatment Session only), and 13 weeks post-injection (i.e., Weeks 13, 26, 39, and 52). The change scores in weight, vital signs, and neurologic exam average score from pre-injection (i.e., Day 1, Weeks 13, 26, and 39) at 4 weeks post-injection (i.e., Weeks 4, 17, 30, and 43), 8 weeks post-injection (i.e., Week 8, first Treatment Session only), and 13 weeks post-injection (i.e., Weeks 13, 26, 39, and 52) will be analyzed, using a paired t-test where applicable, by treatment dose group defined in Section 17.3 for the safety population (i.e., low dose, medium dose, and high dose).

Neurologic exam average score will be summarized descriptively for continuous variable at baseline (Day 1, before first injection of study drug), and post-baseline Weeks 13 and 52. The change scores in neurologic exam average score from baseline at post-baseline time points will be analyzed, using a paired t-test where applicable, by treatment dose group

defined in Section 17.3 for the safety population (i.e., low dose, medium dose, and high dose).

Physical examination will be summarized for abnormal findings at pre-injection of each session and will be reported at post-injection Week 13 (i.e., Weeks 13, 26, 39, and 52), using shift tables.

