Each of the three C-SSRS subscales (suicidal ideation, suicidal behavior, and intensity of suicidal ideation) will be summarized descriptively for continuous variable at each pre-injection visit (i.e., Day 1, Weeks 13, 26, and 39) and at each post-injection time point of 4 weeks post-injection (i.e., Weeks 4, 17, 30, and 43), 8 weeks post-injection (i.e., Week 8, first Treatment Session only), and 13 weeks post-injection (i.e., Weeks 13, 26, 39, and 52).

The change scores in C-SSRS subscales from pre-injection at 4 weeks, 8 weeks (first Treatment Session only), and 13 weeks post-injection will be analyzed, using a paired t-test where applicable, by treatment dose group defined in Section 17.3 for the safety population (i.e., low dose, medium dose, and high dose).

Clinical laboratory tests of hematology, chemistry, and urinalysis (specific gravity and pH) will be summarized descriptively at available visits. Qualitative analysis of laboratory tests in terms of abnormality will be performed, using the shift-table method, for individual post-screening visits. Abnormal findings of clinical laboratory tests for individual subjects will be provided by data listing.

Abnormal findings of dental exam for individual subjects will be provided by data listing.

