17.9 Statistical Methods for Effectiveness

As subjects will receive multiple single-dose injections, each single-dose injection plus its follow-up period will be considered as a treatment session. Post-injection effectiveness endpoints over each of the treatment sessions include USFR, CGI-C, CGI-S, DFSS-I, PGI-C, PGI-S, DIS, and DFSS-S at the injection visit (i.e., Day 1, Weeks 13, 26, and 39), 4 weeks post-injection (i.e., Weeks 4, 17, 30, and 43), 8 weeks post-injection (i.e., Week 8, first Treatment Session only), and 13 weeks post-injection (i.e., Weeks 13, 26, 39, and 52). The pre-injection time points are Day 1 and Weeks 13, 26, and 39 for each of the consecutive treatment sessions. Missing post-injection measurements will not be imputed, whereas missing measurements at the pre-injection of each treatment session will be imputed by the site-specific average of those subjects who receive the treatment at the corresponding treatment session.

For each treatment session, effectiveness analysis of the treatment response will be performed on USFR change from pre-injection, CGI-C, CGI-S, PGI-C, PGI-S, and DIS change from pre-injection, DFSS-I change from pre-injection, and DFSS-S change from

pre-injection at each of the post-injection time points for the ITT population, using a paired t-test. The ITT population will be grouped into three groups by the actual doses the subject received at each session as the following: low dose (2,500 to 2,999 Units), medium dose (3,000 to 3,499 Units), and high dose (3,500 Units).

In addition, the proportion of treatment responders will be reported for the CGI-C and PGI-C at both pre-injection and post-injection time points over each treatment session. Before the analysis, the CGI-C and PGI-C variables will be dichotomized into 2 categories, with “very much improved” and “much improved” into 1 category and the remaining levels in the other category.

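### SAP 2.9 listing dose bands contradict Protocol 17.3 and the SAP's own 2,500-Unit floor, and the 'Any Dose' pooling is not identified as replacing the by-dose analyses of Protocol 17.7 and 17.9

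*SAP*

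**What the plan says.** **Dose range.** Session 1 is given at 3,500 Units. Protocol 13.2 lets the Investigator reduce later sessions after intolerable side effects, and concludes that "the total dose can therefore be 2,500 Units to 3,500 Units of MYOBLOC". SAP 2.9 repeats the limit: "the Investigator had the discretion to decrease subsequent doses, but to no less than a total dose of 2,500 Units".

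**Dose groups in the protocol.** Section 17.3 groups subjects by the dose actually received at each session: "low dose (2,500 to 2,999 Units), medium dose (3,000 to 3,499 Units), and high dose (3,500 Units"). Section 17.9 repeats the same cut-points.

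**Analyses by dose group in the protocol.** Section 17.7 has change scores in weight, vital signs and neurologic exam analysed "using a paired t-test where applicable, by treatment dose group defined in Section 17.3 for the safety population". It says the same of the C-SSRS subscales, where change up to "13 weeks post-injection will be analyzed, using a paired t-test where applicable, by treatment dose group defined in Section 17.3". For effectiveness, Section 17.9 states: "The ITT population will be grouped into three groups by the actual doses the subject received at each session".

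**The SAP.** Section 2.9 reads: "Since the majority of subjects received 3500 Units, all statistical tables will present results under one treatment group labeled" 'Any Dose'. It then adds that "listings will be categorized as L = low dose (1500-2000 U); M = medium dose (2500-3000 U); H = high dose (3500 U"). Section 3.6 separately lists each treated subject's dose.

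**The concern.** Two things in one SAP paragraph do not fit the protocol.

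First, the listing bands use the protocol's names (low, medium, high) with different cut-points. One band cannot hold any dose that the paragraph itself allows. A reader who moves between the protocol and the listings would read the same label as two different doses.

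Second, the tables drop the dose split. A reason is given, but nothing tells the reader that analyses named in the protocol have been replaced. The SAP does say so elsewhere: Section 3.4 states what the protocol indicated and why a smaller change was made. The stake is interpretation. Both objectives name a 3,500-Unit dose, while the later-session tables may include sessions reduced because of poor tolerability, with no column showing 3,500 Units alone.

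**Working it through.** No sample size, power or alpha figure is involved. The check sets the rules side by side.

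**1. Bands.** Inputs: permitted totals of 2,500 to 3,500 Units (Protocol 13.2), protocol groups (17.3) and SAP bands (2.9).

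| Total at a session (Units) | Protocol 17.3 | SAP 2.9 listing |
|---|---|---|
| 1,500 to 2,000 | no group | low |
| 2,001 to 2,499 | no group | no band |
| 2,500 to 2,999 | low | medium |
| 3,000 | medium | medium |
| 3,001 to 3,499 | medium | no band |
| 3,500 | high | high |

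The top of the SAP low band is 2,500 − 2,000 = 500 Units below the floor. Within the permitted range the two schemes agree only at 3,000 and 3,500 Units.

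**2. Dependence on dose steps.** The documents do not say in what steps doses were reduced, so three steps are assumed. These count possible totals, not subjects.

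- 500-Unit steps: 2,500 changes label; no total is without a band.
- 250-Unit steps: 2,500 and 2,750 change label; 3,250 has no band.
- 100-Unit steps: five totals change label (2,500 to 2,900); four have no band (3,100 to 3,400).

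A 2,500-Unit session is labelled differently from the protocol under every step. The gap above 3,000 Units matters only if intermediate totals were given.

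**3. Incomplete sessions.** Per-gland doses in Protocol 13.2 are 1,000 to 1,500 Units per parotid and 250 per submandibular gland.

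- Full totals: 2 × 1,500 + 2 × 250 = 3,500; 2 × 1,000 + 2 × 250 = 2,500.
- One parotid missed: 3,500 − 1,500 = 2,000; 2,500 − 1,000 = 1,500.
- One submandibular gland missed: 3,500 − 250 = 3,250; 2,500 − 250 = 2,250.

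A missed parotid lands in the SAP low band. A missed submandibular gland gives totals with no SAP band, and 2,250 also has no protocol group.

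**4. Pooling.**

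| Analysis | Protocol | SAP |
|---|---|---|
| Weight and vital-sign change | by dose group (17.7) | one group, descriptive (2.9, 2.9.2) |
| C-SSRS change | by dose group (17.7) | one group, descriptive (2.9, 2.9.2) |
| Neurologic exam change | by dose group (17.7) | listing of abnormal findings (2.9.2, 5.8) |
| Effectiveness | three dose groups, paired t-test (17.9) | one group, t-test (2.9, 2.9.1) |
| Treatment-emergent adverse events | by session (17.7) | by session (2.9.2) |

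Adverse-event incidence was never planned by dose, so it is not at issue.

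**5. Where pooling can matter.** In Session 1 every planned dose is 3,500 Units. In a later session let *p* be the fraction treated at a reduced dose. Then

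mean('Any Dose') − mean(3,500) = *p* × [mean(reduced) − mean(3,500)].

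Neither *p* nor the bracket is given in the documents, so the difference cannot be computed. It is zero if no dose was reduced.

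**The case against.** **The bands touch only listings.** This stands. No table, test or estimate uses them, and SAP 3.6 lists the dose itself, so a wrong label can be checked.

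**The low band may be meant for incomplete sessions.** SAP 4.2 scores compliance by how many of four glands were injected, and one missed parotid gives exactly 1,500 to 2,000 Units. This is possible, but the SAP does not say so, and it would not explain the relabelling of 2,500 to 2,999 Units or the unbanded totals. It does show that a repair limited to permitted totals would be too narrow.

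**Pooling is open and within the SAP's remit.** SAP 2.9 recites the reduction rule, states one group and gives a reason. Protocol 17 leaves detailed methods to the SAP. Protocol 17.3 qualifies its grouping, and 17.7 its paired t-test, with *where applicable*. Protocol 11.1 counts doses of 2,500 Units or more together for the safety database. All of this is fair. But the grouping in 17.9 carries no qualifier, and 11.1 also sets a separate count of sixty subjects at 3,500 Units. What remains is that the replacement is not identified.

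**The counts may already be planned.** SAP 3.2 summarises by session the number who received treatment doses, which could mean by dose. The table shells are not in the text available here, so this cannot be settled.

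**Stronger readings a reader might infer.** One is that subjects were dosed below the floor because a 1500 to 2000 U band exists; a band definition is not evidence that anyone fell in it. Another is that many doses were reduced. With the 187 of SAP 2.5 taken as the number treated, a majority is at least 94, leaving up to 187 − 94 = 93. That only restates the word; it estimates nothing. A third is that the pooling was concealed, which its open statement and stated reason contradict.

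**Conclusion.** The point holds in two limited parts.

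The SAP 2.9 bands are wrong as written: they conflict with Protocol 17.3 and 17.9 and with the floor in their own paragraph. The consequence is confined to listing labels. A 2,500-Unit session would be listed as medium where the protocol says low, and any total between 3,000 and 3,500 Units would have no label.

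The pooling is a stated and explained choice, but it is not identified as a change from Protocol 17.7 and 17.9. Because Session 1 is at 3,500 Units by design, saying that most subjects received that dose does not show how many later sessions were reduced. The effect on Session 2 to 4 summaries cannot be sized. The documents do not support saying that it is large, or that it is negligible.

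This rests on the text of Protocol 13.2, 17.3, 17.7 and 17.9 and SAP 2.9 as supplied. SAP 5.12 promises inferential C-SSRS statistics where 2.9.2 describes summaries only. That is a separate inconsistency, to be reconciled on its own. No view is taken on dosing.

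**What to change.** 1. Reconcile the SAP 2.9 bands with Protocol 17.3 so that every total actually administered at a session falls in exactly one band. Provide a separate flagged category for any actual total below the protocol range, for example an incomplete session.
2. State in SAP 2.9 that pooling replaces the by-dose change-score analyses of Protocol 17.7 and the by-dose effectiveness grouping of Protocol 17.9, as Section 3.4 does for its own change.
3. Report the number of subjects by dose band and session, so that the reason given for pooling can be checked.
4. Keep 'Any Dose' as the main column. Add a descriptive 3,500-Unit column to the Session 2 to 4 change tables for effectiveness, vital signs, weight and C-SSRS. Footnote it as a subset selected by tolerability, since it may look better tolerated than the regimen as delivered.

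The cost is SAP wording, one count table (if SAP 3.2 does not already supply it) and a few extra columns. Reduced-dose numbers may be small, so the split should stay descriptive. One extra column restores only part of the protocol's three-group split.

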2.9.1 Effectiveness analysis

As subjects receive multiple single-dose injections, each single-dose injection plus its follow-up period will be considered as a treatment session.

Effectiveness measures obtained over each of the treatment sessions include USFR, CGI-S, CGI-C, DFSS-I, DFSS-S, PGI-S, PGI-C, and DIS at the injection visit (i.e., Day 1, except for CGI-C and PGI-C, and Weeks 13, 26, and 39), 4 weeks post-injection (i.e., Weeks 4, 17, 30, and 43), 8 weeks post-injection (i.e., Week 8, first treatment session only), and 13 weeks post-injection (i.e., Weeks 13, 26, 39, and 52). The injection visit of Day 1 and Weeks 13, 26, and 39 is considered the baseline (or pre-injection), respectively, for each of the consecutive treatment sessions 1 through 4.

For each treatment session, effectiveness analysis of the treatment response will be performed on USFR change from pre-injection, DFSS-I change from pre-injection, and DFSS-S change from pre-injection, CGI-S, CGI-C, PGI-S, PGI-C, and DIS change from pre-injection, at each of the post-injection time points using a t-test.

In addition, the proportion of treatment responders will be reported for the CGI-C and PGI-C at both pre-injection and post-injection time points over each treatment session. Before the analysis, the CGI-C and PGI-C will be dichotomized into 2 categories, with "very much improved" and "much improved" into 1 category and the remaining levels in the other category.

